The study population will consist of participants undergoing RTSA. Eligible participants will be identified at the shoulder and elbow clinic, be invited to take part in the trial, and will be informed of study details and provided with written information along with a detailed explanation of the trial by a member of the research team. Once a participant agrees to participate, and meets all inclusion criteria, they will be enrolled and randomized into one of two groups.

Study participants

Inclusion criteria

- All patients undergoing primary RTSA

Exclusion criteria

- Revision RTSA
- RTSA for acute proximal humerus fracture or fracture sequela

Baseline measures

The following will be collected from all participants preoperatively:

- Age
- Sex
- Preoperative functional (operative) shoulder and contralateral shoulder range of motion if applicable
- Indication for RTSA
- Associated injuries
- Medical comorbidities
- Residence and ambulatory status

Treatment allocation

Individuals consenting to participate in the trial will be randomized to RTSA or RTSA plus conjoint tendon lengthening. Each patient will receive a study ID, and a computer randomization system will be used to allocate patients to receive either of two groups.

Intervention

All RTSAs will be performed by the attending surgeon ([name]) in a standard fashion through a deltopectoral approach. The skin will be incised with bovie electrocautery in standard fashion, and the dissection will be carried down through the subcutaneous tissue to the level of the shoulder. The subscapularis muscle will be incised and reflected to expose the shoulder joint. Following

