surgical removal of the humeral head and reaming of the glenoid cavity, the Perform glenoid and humeral components of Tornier Stryker Reverse Shoulder system will be implanted. The sizes and offsets of the components will be chosen based on each patient's local anatomy which will vary among patients. Each of these surgical steps will be performed in all patients regardless of whether they are in the control or investigative group. Following final implant selection, the subscapularis tendon will be repaired using three transosseous nonabsorbable sutures whenever there is a repairable subscapularis tendon. After definitive implantation of the prosthesis is completed, and the subscapularis tendon is reattached, the investigative step will take place. In the control group, which is the group receiving a RTSA without conjoint tendon lengthening the subcutaneous tissue and skin will be closed in standard fashion. In the investigative group, prior to subcutaneous and skin closure, the conjoint tendon will be lengthened by approximately 2 cm. The conjoint tendon is comprised of the coracobrachialis and biceps short head tendon, which attach proximally to the coracoid process at the level of the shoulder. In the investigative group, as mentioned, the conjoint tendon will be released completely via a Z-shaped incision made at a level 2 cm distal to the coracoid process and sutured back in a lengthened position using #2 Ethibond suture for the patients assigned the conjoint lengthening group. Electrocautery will be used for the lengthening, and the underlying muscular portion of the conjoint tendon will be preserved. As mentioned above, the control group will not receive this conjoint tendon lengthening. Then, for the investigative group following lengthening and like the control group, the wound will be closed in layers, and the shoulder will be immobilized in an abduction sling.

Postoperative management

Postoperatively, patients will wear the sling for 4 weeks, after which supervised physical therapy will begin.

Outcome measures

The primary outcome will be functional internal rotation at six months. Functional internal rotation will be measured based on the highest anatomical level that the patient's thumb can reach:

- Side
- Ipsilateral buttock
- Lower lumbar
- Mid-lumbar
- Upper lumbar
- Thoracolumbar junction
- T10 and above

Additional secondary outcome measures and associated timepoints will include:

- Six weeks: pain VAS

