- Three months: pain VAS, ASES, SANE, Forward elevation, external rotation at the side
- Six months, one year, and two years: pain VAS, ASES, SANE, PROMIS, VR-12, Forward elevation, external rotation at the side
- Complications at any time points: dislocation, severe pain, arm muscle cramping, implant loosening, infection, hematoma, medical complications, blood transfusions, non-union, mortality rate. Specific surgical complications include wound infections, intraoperative fracture, deep surgical infection, and periprosthetic fractures.

Follow-up

All participants will be surveilled per standard of care at our hospital for the targeted patient group. Patients will return for follow-up at two weeks, six weeks, three months, six months, one year, and two years. Plain radiographs will be taken at the immediate postoperative (anesthesia care unit) setting and at all scheduled follow-up visits. Radiographs obtained in clinic at the aforementioned follow-up intervals are standard of care and are not part of the research explicitly. For example, all patients regardless of whether they are in the control or investigative group will receive radiographs at the above intervals. A member of the research team will review participant outcome measures at each appointment.

Sample size calculation

To reject the null hypothesis that functional internal rotation is equal between groups, 32 subjects are needed per group with a power set at 80%, and with a Type 1 error probability of 5%.

Data collection and management, and risks

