Data collection will primarily be electronically based. A breach of confidentiality and/or privacy is a risk of this study. To prevent this, all collected data will be stored electronically in password-protected files to protect patient identity and information. All information will be collected and reviewed by the research team only. Data will be maintained on a password-protected computer that will be accessible only to the study team. No patient identifiers will be maintained in the database. Every attempt will be made to minimize missing data. Multiple contact details will be taken at recruitment, and a system of reminders plus phone contact if applicable will be made to ensure patients make follow-up appointments. Additionally, there is an additional risk of being withdrawn from the Standard of Care treatment if they are randomized into the experimental condition. Benefits of this procedure included improved functional internal rotation following surgery and the potential to change clinical practice.

Data analysis

The primary outcome (i.e., functional internal rotation at six months) will be compared between the groups using Mann-Whitney U test. Other range of motion data (i.e., forward elevation and external rotation at the side), pain VAS, ASES, SANE, PROMIS, and VR-12 will be compared using either independent t-test or Mann-Whitney U test depending on the normality of data distribution of each variable. The correlations between functional internal rotation and all other variables will be analyzed using Spearman rank correlation or Pearson correlation.

Patient and public involvement

Patients who undergo RTSA often have limitation of functional shoulder internal rotation following surgery. However, there are no literature that discuss conjoint tendon lengthening as a possible therapeutic intervention. The current research question was developed to address this, and patients were not involved in the design, recruitment, or conduct of this study. The future results of this trial will be available through publication in a peer-reviewed journal, and at meetings if applicable.

ETHICS AND DISSEMINATION

Safety

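### An undefined normality check picks the test for the secondary motion and score outcomes, visits of one score need not share a test, and collected preoperative motion is not used for adjustment

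*Combined protocol and SAP*

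**What the plan says.** The Data analysis section sets the primary comparison in advance: functional internal rotation at six months "will be compared between the groups using Mann-Whitney U test". For forward elevation, external rotation at the side, pain VAS, ASES, SANE, PROMIS and VR-12 it says that they "will be compared using either independent t-test or Mann-Whitney U test depending on the normality of data distribution of each variable". It names no normality test, no cut-off, and no unit of assessment (each arm, both arms pooled, each visit).

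The Outcome measures section schedules these outcomes repeatedly:
- The first of these visits has pain only: "Six weeks: pain VAS"
- The next one adds two scores and both motion outcomes: "Three months: pain VAS, ASES, SANE, Forward elevation, external rotation at the side"
- The last three visits carry all seven outcomes: "Six months, one year, and two years: pain VAS, ASES, SANE, PROMIS, VR-12, Forward elevation, external rotation at the side"

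The Baseline measures section lists "Preoperative functional (operative) shoulder and contralateral shoulder range of motion if applicable". It lists no preoperative VAS, ASES, SANE, PROMIS or VR-12. The Data analysis section names no adjusted, change-from-baseline or repeated-measures comparison between the arms. The only other place where baseline motion might appear is the correlation analysis: "The correlations between functional internal rotation and all other variables will be analyzed using Spearman rank correlation or Pearson correlation".

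**The concern.** The t-test compares means and the Mann-Whitney test compares ranks. If the data choose between them, the quantity reported for a score is not known until the data are in. Because the plan does not tie all visits of a score to one choice, ASES could be reported as a mean difference at six months and as a rank comparison at one year, and the two results could not be read as a course over time. An undefined check also leaves room for judgement after the data have been seen.

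The second part concerns precision. Forward elevation and external rotation are measured after surgery in 64 patients whose preoperative motion is on file. Comparing follow-up values alone leaves the between-patient variation that the preoperative value could explain in the error term.

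**Working it through.** **The plan's own figure.** The Sample size calculation section gives 32 per group, 80% power and 5% type 1 error, for the primary outcome, with no effect size, SD or sidedness. It can therefore only be solved backwards. Two-sided, normal approximation: d = (1.960 + 0.842) × √(2/32) = 2.80 × 0.25 = 0.70 SD. The point below uses only the 32 per arm and does not depend on how it was derived.

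**Number of comparisons.** Six weeks 1; three months 5; six months, one year and two years 7 × 3 = 21. Total 1 + 5 + 21 = 27, counting PROMIS and VR-12 as one score each. Each outcome is measured at 3 to 5 visits.

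**Behaviour of the rule.** The plan names no check, so one was assumed: t-test if Shapiro-Wilk p > 0.05 in both arms, otherwise Mann-Whitney. There were 32 per arm and 4,000 simulated datasets per setting. The distributions are assumptions.

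| Distribution, no arm difference | t-test chosen | Type I error: rule | t-test alone | Mann-Whitney alone |
|---|---|---|---|---|
| Normal | 90.2% | 5.0% | 4.8% | 4.7% |
| Gamma, skewness 0.7 | 53.6% | 4.8% | 4.6% | 4.4% |
| Gamma, skewness 1.0 | 28.6% | 5.5% | 5.2% | 4.9% |
| Exponential | 0.0% | 5.3% | 5.0% | 5.3% |

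Three things follow:
1. The rule does not materially disturb type I error.
2. The t-test alone also holds its level in these settings, so the check is not needed to protect it.
3. With moderate skewness, chance decides which test is used.

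The choice can matter for a single result. At a true shift of 0.7 SD the two tests disagree on significance in about 6% of datasets (normal, or skewness 0.7), 9% (skewness 1.0) and 16% (exponential). Taking the smaller of the two p-values would give a type I error of 5.6–7.3%. The plan does not propose this; it bounds what free choice between these two tests could do.

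**Precision from baseline motion.** For a linear model adjusted for the preoperative value, residual variance = σ²(1 − r²), where r is the correlation between the preoperative and follow-up values. The documents give no r; 0.3 to 0.6 is assumed.
- r = 0.3: variance falls by 0.3² = 9%; the SE is multiplied by √0.91 = 0.954; this equals 32/0.91 ≈ 35 per arm unadjusted.
- r = 0.6: variance falls by 0.6² = 36%; the SE is multiplied by √0.64 = 0.80; this equals 32/0.64 = 50 per arm unadjusted.

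With all 64 patients followed, the half-width of the 95% CI for an arm difference is about 1.96 × √(2/32) = 0.49 SD unadjusted. It becomes 0.49 × 0.954 = 0.47 SD at r = 0.3 and 0.49 × 0.80 = 0.39 SD at r = 0.6.

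**The case against.** The strongest reply is that the rule speaks of each variable, and the same sentence lists its variables as scores, not as scores at visits. One test per score is a natural reading, and under it the switching between visits disappears. That stands as far as it goes: switching is permitted by the text, not stated by it. The check remains undefined under either reading.

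A reader might infer that most trials run this way would mix tests within a score. The documents do not support a figure. With four independent visits the chance of mixing is 1 − c⁴ − (1 − c)⁴, where c is the chance that the t-test is chosen. Its ceiling is 87.5%, at c = 0.5. It is about 34% for normal data and 0% for exponential data, and correlation between visits changes it again.

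A reader might also infer that the check inflates false positives. It does not. When means are equal but spreads differ, the rule can reject well above 5%, but the excess belongs to the Mann-Whitney test, which does not test equality of means. With gamma data of shape 4 and a spread ratio of 2, the t-test rejected in 5.4% of runs, Mann-Whitney alone in 10.3% and the rule in 10.2%.

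Three further points stand in the plan's favour. The Study design section has an independent statistician blinded to allocation, which limits steering of the test choice, though it does not define the rule. An unadjusted comparison in a randomized trial is valid, so adjustment is a gain and not the repair of an error. Baseline is listed only for motion, so adjustment is available for two of the seven outcomes; a mixed model for every score would be partly a matter of preference. The correlation analysis may use baseline motion, but it is not a comparison of the arms.

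**Conclusion.** The point holds in a limited form. For seven secondary outcomes the test depends on an undefined look at the data, and the plan does not ensure that a score is compared on the same scale at every visit. For two of the seven, a baseline value that the trial already collects is left out of the arm comparison. The type I error of the rule stays near 5% and the primary analysis is untouched, so this concerns interpretability and precision, not validity.

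The gain from adjustment is a variance reduction of 9–36%, which rests on an assumed r of 0.3–0.6. It also assumes that the preoperative range of motion includes forward elevation and external rotation of the operative shoulder; the baseline list does not name the movements. The simulated figures rest on an assumed Shapiro-Wilk check and assumed distributions. Complications, which have no test named, are outside this point.

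**What to change.** Replace the normality-dependent choice in the Data analysis section with one pre-specified method per outcome, used at all visits:
- **Forward elevation and external rotation:** a linear model (ANCOVA at each visit, or one repeated-measures model) with arm and the preoperative value of the same movement. Report the arm difference with a 95% CI, with six months as the main secondary estimate, in line with the primary time point. Keep Mann-Whitney as a sensitivity analysis.
- **Pain VAS, ASES, SANE, PROMIS and VR-12:** no baseline is listed, so name one unadjusted comparison per score for all visits. A mixed model is optional.
- **Baseline measures:** state that forward elevation and external rotation of the operative shoulder are among the preoperative movements recorded.

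The change should be made before outcome data are examined. It needs no extra patients or visits. It costs a wording change, slightly more analysis work, and reliance on a linear model for the motion outcomes. Fixing one test per score also has a price: a t-test fixed for a score that proves strongly skewed would lose power. In the exponential setting at a shift of 0.7 SD it had 78.8% power, against 94.5% for Mann-Whitney. The choice for each score should therefore be made with its expected distribution in mind.

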Any protocol modifications will be reported to the IRB, trial registry, protocol database, and individual participants. All adverse events will be reported to the IRB committee as well, and confidentiality of individuals involved in the trial will be maintained as discussed above.

Dissemination

The results of the study will be presented at national orthopaedic meetings and the results will be published in an orthopaedic, biomechanical, or surgical research journal following completion of the trial.

DISCUSSION

A recently study by Horchreiter et al.¹⁴ found that active extension of at least 40° is a prerequisite for satisfactory functional internal rotation after RTSA, with an average loss of 16° of active extension following RTSA compared to the contralateral unaffected side. Our clinical and biomechanical observation is that the conjoint tendon becomes tight with extension, which appears to be the main limiting factor for extension and ultimately internal rotation after RTSA. Based on this observation and the study by Horchreiter et al., we hypothesize that the conjoint tendon is a factor limiting extension and internal rotation after RTSA, and that releasing/lengthening the conjoint tendon may increase extension and affect the prosthetic joint biomechanics. To this end, we proposed a prospective randomized clinical trial in which we will randomize patients who undergo primary RTSA into two groups, conjoint tendon lengthening group vs. control group, and compare various clinical outcome measures including functional internal rotation at multiple postoperative time points. We hypothesized that conjoint tendon lengthening will have significantly greater extension and functional internal rotation of the shoulder following RTSA compared to the control group. This trial has the capacity to find a safe and effective way to improve functional internal rotation after RTSA. If so, a novel surgical application of this concept may lead to a substantial improvement in the disabling limitation of internal rotation following RTSA. Limitations of this study include the lack of blinding of surgeon, participants, and research assessors who have access to operative notes. Blinding was not used in this study as it is impossible to blind the participating surgeon to operative technique.

